## Evaluation of Angle Kappa and Different Intraocular Lens Calculation Formulas in Acrysof® IQ PanOptix Intraocular Lens Outcomes, Visual Disturbances and Patient Satisfaction

#### **INTRODUCTION**

Current visual outcomes expectations of cataract patients are similar to those of refractive surgery patients. Their desire is to be spectacle independent for far, intermediate and near vision activities. Some may have already enjoyed freedom from glasses and would like to continue after the cataracts are removed. Different options are available. These options include: mono-vision and presbyopia correcting intraocular lenses (IOL).

Mono-vision can be achieved by setting the non-dominant eye to -1.75 (range may vary according to patient's preference -1.25 to -2.50 D) and the dominant eye to plano at time of cataract surgery, or postoperatively using contact lenses, or undergoing LASIK. Presbyopia correcting IOLs include accommodative, multifocals, extended depth of focus (EDOF) and the recently approved trifocal IOLs.

Accommodative IOLs are design to expand the range of vision by emulating accommodation. The lens is designed to allow the lens optic to move slightly forward with the contraction of the ciliary muscle. The only accommodative IOL approved in the USA is the Crystalens (Bausch and Lomb). In addition to the non-toric model, there is a toric version (Trulign) that is ideal for patients who also have astigmatism. Different studies have shown limited accommodation (0.25 to 0.75 D), which is not optimal, leading surgeons to target slight residual myopia (-0.50 to -0.75) in the non-dominant eye. Tilting and decentration of the IOL due to contraction and fibrosis of the capsular bag have also been reported.

Multifocal IOLs (MIOL) have evolved since they were initially approved by the FDA in 1997 (Array SA40N, Abbott Medical Optics). MIOL have been classified based on their design as refractive or diffractive. Refractive MIOL (i.e ReZoom, Abbot Medical Optics) reportedly provided better intermediate vision compared to a diffractive MIOL (i.e ReSTOR, Alcon Laboratories) that provides better near visual acuity. Mixing and matching these 2 lenses was an option to overcome the limitations that each one presented providing patients with improved intermediate and near acuities. The ReSTOR has been modified while the ReZoom IOL was discontinued 2 - 3 years ago. The original ReSTOR had a +4.0 D add delivering good uncorrected distance and uncorrected near visual acuities (UCDVA and UCNVA) with a reading distance of 33 cm but with limited intermediate acuity. Two additional ReSTOR models are currently available in the market, a +3.0 D add to enhance the intermediate distance vision with a reading distance of 40 cm, and a +2.5 D add ideal for people who are interested in distance and intermediate vision (50 - 60 cm) activities. One potential disadvantage of the low add multifocal IOLs is the visual performance at near. Similarly, to mixing and matching, the use of a ReSTOR +3.0 in one eye and

[name]

the +2.5 in the fellow eye, known as blended vision, is an option to improve patients' vision at the different distances reducing their dependence on glasses.

Trifocal IOLs (a type of MIOL), specifically the PanOptix IOL, have been widely use in Europe, Canada and South America and was approved in the USA by the U.S. Food and Drug Administration (FDA) on August 27, 2019. Since its approval, it is becoming the presbyopia correcting lens of choice in the US. Because of the way the lens is designed, it provides good intermediate vision without compromising the near or the distance visions overcoming the limitation that previous multifocal lenses presented.

The main complaint of patients who received a MIOL (regardless of the design) are visual disturbances such as glare, halos (rings around lights), starbursts (rays around light sources), mainly at night. The degree of limitation or how bothered patients are varies from patient to patient. To explain these symptoms different theories have been proposed including splitting the light into different focal points which decreases the intensity of the light reaching the retina. Most factors are common to all patients who received the lens; however, patients are not equally affected by these symptoms. Angle kappa has been considered a factor. Angle  $\kappa$  is the angle between the visual axis (straight line that passes through both the center of the pupil and the center of the fovea) and the pupillary axis (perpendicular line to the surface of the cornea that passes through the center of the pupil), figure 1. The larger the angle kappa the more symptoms.

#### 1. OBJECTIVE:

The purpose of this study is to evaluate the effect of angle kappa in outcomes, patient satisfaction and visual disturbances in patients with and without astigmatism implanted bilaterally with the PanOptix toric and non-toric IOL after routine cataract surgery as well as to evaluate intraocular (IOL) calculation formulas.

#### 2. STUDY DESIGN AND METHODS:

- **2.1. Test article:** AcrySof® IQ PanOptix IOL (TFNT00 and TFNTx0 Alcon Laboratories).
- **2.2. Study Design:** Prospective, single center, bilateral eye study.

#### 2.3. Subjects:

#### 1. Inclusion Criteria:

Subjects MUST fulfill the following conditions to qualify for enrollment into the trial

- 1. Subject is undergoing bilateral lens extraction with intraocular lens implantation.
- 2. Gender: Males and Females.
- 3. Age: 40 years and older.
- 4. Willing and able to provide written informed consent for participation in the study

- 5. Willing and able to comply with scheduled visits and other study procedures.
- 6. Scheduled to undergo standard cataract surgery with topical anesthesia in both eyes within 6 to 30 days between surgeries.
- 7. Subjects who require an IOL power in the range of +6.0 D to +30.0 D only.
- 8. Subjects who require a TFNT00 or TFNT30 to TFNT60 IOL.
- 9. Potential postoperative visual acuity of 0.2 logMAR (20/32 Snellen) or better in both eyes.

#### 2. Exclusion Criteria:

Subjects with ANY of the following conditions on the eligibility exam may NOT be enrolled into the trial.

- 1. Severe preoperative ocular pathology: amblyopia, rubella cataract, proliferative diabetic retinopathy, shallow anterior chamber, macular edema, retinal detachment, aniridia or iris atrophy, uveitis, history of iritis, iris neovascularization, medically uncontrolled glaucoma, microphthalmos or macrophthalmos, optic nerve atrophy, macular degeneration (with anticipated best postoperative visual acuity less than 20/30), advanced glaucomatous damage, etc.
- 2. Subjects who require a higher toric power than the one available (TFNT60).
- 3. Uncontrolled diabetes.
- 4. Use of any systemic or topical drug known to interfere with visual performance.
- 5. Contact lens use during the active treatment portion of the trial.
- 6. Any concurrent infectious/non-infectious conjunctivitis, keratitis or uveitis.
- 7. Clinically significant corneal dystrophy
- 8. History of chronic intraocular inflammation.
- 9. History of retinal detachment.
- 10. Pseudoexfoliation syndrome or any other condition that has the potential to weaken the zonules.
- 11. Previous intraocular surgery.
- 12. Previous refractive surgery.
- 13. Previous keratoplasty
- 14. Severe dry eye
- 15. Pupil abnormalities
- 16. Anesthesia other than topical anesthesia (i.e. retrobulbar, general, etc).
- 17. Any clinically significant, serious or severe medical or psychiatric condition that may increase the risk associated with study participation or may interfere with the interpretation of study results.
- 18. Participation in (or current participation) any ophthalmic investigational drug or ophthalmic device trial within the previous 30 days prior to the start date of this trial.

The principal investigator reserves the right to declare a patient ineligible or non-evaluable based on medical evidence that indicates the patient is unsuitable for the trial.

#### 3. Study Procedures

#### 3.1. Informed Consent / Subject enrollment

Potential subjects will be identified from the patients presenting at the clinic. Additionally, a flyer will be placed in the check-in area of the different locations and on the practice website. Once identified as a study candidate, the patient will be asked if he/she would like to participate. The sub-investigator, study coordinator or an appropriately trained staff member will answer any and all questions and will obtain informed consent. A copy of the signed informed consent document will be given to the subject. The principal investigator will be available if the subject wants to discuss further details with him. Any testing that is part of the investigative site's standard preoperative cataract evaluation may be performed prior to the informed consent being signed, provided these tests are conducted within 90 days of surgery. The patient will understand that participation in the study, or declining to participate, will not affect his/her quality of care.

No subject will be enrolled into the study that does not meet the inclusion/exclusion criteria and does not sign the current approved informed consent document. Informed consent will be obtained prior to collecting any data for the study. The original signed documents will be maintained by the investigator as a permanent part of the subject's research records and a copy will be provided to the patient.

#### 3.2. Surgery Procedures:

[figure not shown]
Patients will be received either a non-toric or toric PanOptix IOL based on the amount of astigmatism. Target refraction OU plano ( $\pm 0.25$  D).

#### **3.3. Study Visit Schedule and Assessments** (Table 1).

- 1. **Visit Schedule:** Subjects will be examined at the following intervals:
  - 1. Visit 1: Screening and enrollment: Preoperative evaluation completed not more than eight weeks before surgery
  - 2. Visit 2: Day of Surgery for each eye
  - 3. Visit 3: Month 3: 90 ±15 days postoperative after second eye surgery

#### 3.4. Measurements and evaluations

1. Visit 1: Informed consent process will be conducted at this visit. Assessments include best-corrected Snellen visual acuity, manifest refraction, intraocular pressure (IOP) using Goldman tonometer, slit lamp examination including dilated fundus exam,

- 2. Visit 2: The surgeon may use his preferred cataract extraction technique (manual or laser). The lens will be implanted in the bag. The following information will be captured the day of surgery: phaco technique (manual or laser), lens implanted and power, target refraction for IOL power implanted using Barrett Universal II, Hill RBF, Holladay 2, Holladay 1 and SRK-T formulas, residual astigmatism and axis for Barrett Toric Calculator and Barrett TK for toric power calculation (if applicable), additional surgical procedures, intraoperative complications, and any device deficiencies. The surgeon's standard post cataract surgery treatment will be used in all patients.
- 3. Visit 3: Slit lamp examination, manifest refraction, UCVA, BCVA, UCIVA (at 60 cm), DCIVA (at 60 cm), UCNVA (at 40 cm) and DCNVA (at 40), and UCNVA at best distance, IOP, IOL orientation, dilated fundus exam (as deem necessary by the investigator), angle kappa measured using OPD III scan, visual symptoms, patient satisfaction and spectacle independence questionnaires, adverse events and any device deficiencies.

All adverse events and complaints will be monitored and recorded at all study visits.

**Table 1.** Visits and Study Assessments

	Visit 1 Screening	Visit 2 and 2A DOS	Visit 3 3-Month 90 ±15 days
Informed Consent	X		
Inclusion/Exclusion	X	X	
Demographics/PMH/Ocular history	X		
Snellen BCVA	X		
Snellen Manifest refraction	X		
UCVA ETDRS (4m)			Χ*
Manifest refraction – Max Plus			X
BCVA ETDRS (4m)			Χ*
UCIVA ETDRS (60 cm)			Χ*
DCIVA ETDRS (60 cm)			Χ*

UCNVA ETDRS (40 cm)			X*
DCNVA ETDRS (40 cm)			Χ*
UCNVA at best distance			Χ*
Intraocular Pressure (Goldman)	X		X
SLE	X		X
Dilated fundus exam	X		χ†
Cataract density / type	X		
OPD III scan	X		X
IOL Power calculation using different formulas	X		
Toric IOL calculation	X**		
Intraoperative data		X	
Toric IOL position		X**	χ†
Questionnaires	X		X
AE/Device deficiencies		X	X

8

X To be performed as scheduled

- \* Monocular and binocular testing
- \*\* If a toric lens is used
- † To be performed as deem necessary by the investigator

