#### 2. Secondary Endpoints:

- a. Proportion of eyes within ±0.50 D of intended target (plano) when using the Barrett Universal II formula for IOL power calculation
- b. Proportion of eyes within  $\pm 0.50$  D of intended target (plano) when using the Hill RBF formula for IOL power calculation
- c. Proportion of eyes within ±0.50 D of intended target (plano) when using the Holladay 2 formula for IOL power calculation
- d. Proportion of eyes within ±0.50 D of intended target (plano) when using the Holladay 1 formula for IOL power calculation
- e. Proportion of eyes within ±0.50 D of intended target (plano) when using the SRK-T formula for IOL power calculation
- f. Proportion of eyes with residual astigmatism of 0.50 D or less when using the Barrett Toric Calculator
- g. Proportion of eyes with residual astigmatism of 0.50 D or less when using the Barrett TK for toric power calculation

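### Secondary endpoints f and g do not say whether residual astigmatism is predicted or achieved, and on no reading do they test the two toric calculators against outcome; the Visit 3 toric axis rule also needs one clear wording.

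*Combined protocol and SAP*

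**What the plan says.** - **Objective (section 1).** Besides the effect of angle kappa, the study is intended "as well as to evaluate intraocular (IOL) calculation formulas".
- **Endpoints (section 5.3, secondary endpoints f and g).** "Proportion of eyes with residual astigmatism of 0.50 D or less when using the Barrett Toric Calculator" and "Proportion of eyes with residual astigmatism of 0.50 D or less when using the Barrett TK for toric power calculation". These are the only toric calculator endpoints.
- **Data at Visit 2 (section 3.4).** The day-of-surgery record includes "residual astigmatism and axis for Barrett Toric Calculator and Barrett TK for toric power calculation (if applicable", so both calculators' outputs are captured for the same eye.
- **Data at Visit 3 (Table 1).** "Manifest refraction – Max Plus" is scheduled with no discretion mark.
- **Toric axis at Visit 3.** The section 3.4 text lists "IOP, IOL orientation, dilated fundus exam (as deem necessary by the investigator", with the bracket closing there. Table 1 puts a dagger on two Visit 3 rows, the dilated fundus exam and the toric lens position. The dagger means "To be performed as deem necessary by the investigator". At Visit 2 the same position row applies to every toric eye.
- **Lens choice and allocation.** Section 3.2 chooses toric or non-toric by the amount of astigmatism and names no deciding calculator. Section 8.3, on assigning subjects, is not applicable.
- **Analysis (sections 5.1 and 5.2).** Thirty subjects, a rule-of-thumb pilot size, descriptive statistics. No prediction error is defined.

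**The concern.** An endpoint meant to evaluate a calculator has to set what it predicted against what happened. Endpoints f and g apply a 0.50 D limit to a residual without saying whose residual it is. The analyst must choose a meaning after the data are in, and none of the available meanings answers the question in the objective. A report could then show two similar percentages and be taken as evidence that the calculators perform equally well.

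The Visit 3 axis raises a smaller, separate question. A site that follows Table 1 may leave the axis unrecorded; one that reads the section 3.4 text plainly would record it in every toric eye. The axis would help to separate calculator error from lens rotation, but only once a prediction-error endpoint exists.

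**Working it through.** The plan gives no figure to reproduce here: 30 is a flat rule, and no SD, lens cylinder in dioptres or number of toric eyes is stated. Inclusion criterion 8 names only models ("Subjects who require a TFNT00 or TFNT30 to TFNT60 IOL"). The ceiling is 30 × 2 = 60 eyes. The objective expects eyes with and without astigmatism, so the toric count should lie between the extremes.

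**Step 1. The possible readings of f and g.**

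| Reading | Source of the value | What f and g show |
|---|---|---|
| Predicted residual | Visit 2 calculator output | May differ, but no outcome enters |
| Achieved residual, all toric eyes | Visit 3 manifest refraction | One lens and one residual per eye: they differ in 0 of the eyes counted under both |
| Achieved residual, only eyes whose lens was chosen with that calculator | Visit 3, by subgroup | No deciding calculator named and no assignment made: groups undefined |

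The second row needs no assumption.

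**Step 2. What a prediction error would show.** All error sizes here are assumed, for illustration. If both components of an astigmatism vector are normal with mean 0 and SD s, the proportion with length at most 0.50 D is 1 − exp(−0.50² / (2s²)).

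- Achieved residual, s = 0.3 D: 1 − exp(−0.25/0.18) = 75.1%. This is both f and g, however accurate either calculator is.
- Prediction error, calculator A with s = 0.2 D: 1 − exp(−0.25/0.08) = 95.6%.
- Prediction error, calculator B with s = 0.4 D: 1 − exp(−0.25/0.32) = 54.2%.

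So a twofold difference in error SD is invisible in the achieved residual and plain in the prediction error.

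Predicted values can mislead in another way. Let both calculators' predictions have s = 0.2 D, with the outcome equal to A's prediction plus an error of SD 0.2 D, and B's prediction unrelated to the outcome. Predicted residuals give 95.6% for each. Prediction errors give 95.6% for A. For B the variance is 0.04 + 0.04 + 0.04 = 0.12, so 1 − exp(−0.25/0.24) = 64.7%.

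**Step 3. The role of the axis.** Suppose a lens of corneal-plane cylinder C exactly matches the cornea and then rotates by θ. The residual is 2C·sin θ, which reaches 0.50 D at θ = arcsin(0.25/C). For assumed C of 1.0, 1.5, 2.0 and 2.5 D, that is 14.5, 9.6, 7.2 and 5.7 degrees. Rotation can therefore matter at the chosen limit.

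However, when both calculators' predictions refer to the same implanted lens at the same intended axis, rotation adds the same vector to both errors. Adding it by simulation, uncorrected, to calculators A and B of step 2:

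| Assumed C and rotation SD | A within 0.50 D | B within 0.50 D | Gap (points) |
|---|---|---|---|
| No rotation | 95.6% | 54.2% | 41.4 |
| 1.5 D, 5 degrees | 81.8% | 47.8% | 34.0 |
| 2.5 D, 8 degrees | 46.5% | 30.9% | 15.6 |

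Both proportions fall and the gap narrows, but the order holds in these cases.

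**The case against.** The best defence is that the plan promises no head-to-head test. It says it will evaluate the formulas, descriptively, in a pilot, and the data needed are already scheduled. This stands as a limit on severity: the fault is in how two endpoints are defined, and a reader who concludes that the study cannot evaluate the calculators goes further than the documents allow. It does not rescue f and g, because even a descriptive evaluation has to bring prediction and outcome together.

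Two stronger readings of the axis issue are tempting.

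- *That Table 1 and the section 3.4 text contradict each other.* The bracket directly follows only the dilated fundus exam, but it could be read to cover the lens orientation before it. That would match the two daggers in Table 1. Nor do the documents say that lens orientation and toric lens position are the same measurement. This is an ambiguity, not a definite contradiction.
- *That without the Visit 3 axis the calculators cannot be compared.* Endpoints f and g do not use the axis, so recording it in every toric eye would not repair them. With a prediction-error endpoint, a missing axis lowers the absolute accuracy figures and narrows the gap, but the comparison remains possible.

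**Conclusion.** The point holds as a minor one with a cheap improvement. As worded, f and g do not evaluate either toric calculator against outcome on any of the three readings. The firmest part is arithmetic: with achieved values, f and g differ in 0 of the eyes counted under both. The percentages in the working rest on assumed error sizes, lens cylinders and rotation SDs, and show direction only. The shared-rotation argument also assumes that both calculators' recorded predictions are for the implanted lens at one common intended axis, which the plan does not spell out.

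The Visit 3 axis wording is an ambiguity to settle and has no effect on f and g as they stand. The other five secondary endpoints are outside this point, and the primary endpoint is unaffected.

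**What to change.** 1. Redefine f and g as the proportion of toric eyes, for each calculator, whose vector prediction error is 0.50 D or less. The error is the Visit 3 manifest refractive astigmatism minus the residual astigmatism and axis that the calculator predicted at Visit 2 for the implanted lens, as a vector difference. State that both predictions refer to the same lens and intended axis. Compare the calculators within eye, and describe how two eyes from one subject are handled.
2. Report achieved residual astigmatism of 0.50 D or less once, as a lens outcome.
3. Reconcile Table 1 with the section 3.4 text on the Visit 3 toric axis, and say whether the two names mean the same measurement. Where an axis is recorded, also report the error with the prediction shifted to it: predicted residual at the planned axis, plus the lens cylinder vector at the planned axis, minus that vector at the measured axis.

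**Cost.** Items 1 and 2 change the wording of two descriptive endpoints and add a little vector analysis to data already scheduled. The supplementary analysis in item 3 needs either the implanted lens's corneal-plane cylinder or a calculator rerun at the measured axis; neither is listed now. In eyes without a recorded axis, the proportions will include rotation error, and the report should say so.

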#### 4. Study endpoint criteria

- 4.1. Patient Completion of Study: If a study patient has completed the final visit (Visit 3) of the study, he/she is considered to have completed the study.
- 4.2. Patient Discontinuation: Each study patient may voluntarily discontinue the study at any time they choose. Study patients who cannot complete the study for administrative reasons (e.g., non-compliance, failure to meet visit schedule, etc.) will be discontinued from the study. Study patients discontinued during the enrollment phase (prior to surgery) of the study will be replaced.
- 4.3. Patient Termination: A study patient will be terminated if the study patient develops any severe adverse event that may be related to the study. A study patient will receive appropriate treatment at the discretion of the investigator. Notification of termination will be clearly documented. These study patients are considered to have completed the study and will not be replaced.
- 4.4. Study Termination: The investigator with appropriate notification may terminate the study. If, after clinical observations, the investigator feels that it may be unwise to continue the study, he may stop the study.

9

4.5. Study Completion: The study will be complete when all enrolled patients have completed Visit 3 or have been terminated from the study.

#### 5. STATISTICAL CONSIDERATIONS

#### 5.1. Sample size

A total of 30 subjects will be enrolled. In order to calculate the sample size, we need to know an accurate estimate of the standard deviation of the outcome measure which we do not know; therefore, we consider this study a pilot trial. When estimating the sample size for a pilot study, the simplest method is to apply a sample size rule of thumb. Browne suggests a general flat rule to 'use at least 30 subjects or greater to estimate a parameter'.

